7.1.1 Temporary Discontinuation

For participants needing treatment with prohibited concomitant medications, study drugs must be discontinued or interrupted temporarily.

For decisions around discontinuation, the Study Physician can be consulted as appropriate.

7.2 Participant Withdrawal from the Study

- A participant may withdraw from the study at any time at his/her own request, or may be withdrawn at any time at the discretion of the Investigator for safety, behavioural, compliance, or administrative reasons. This is expected to be uncommon.
- A participant who considers withdrawing from the study must be informed by the Investigator about modified follow-up options (eg, telephone contact, a contact with a relative or treating physician, or information from medical records).

- At the time of withdrawal from the study, if possible, an Early Study Drug Discontinuation Visit should be conducted, as shown in the SoA. See SoA ([Table 1](#)) for the data to be collected at the time of study withdrawal and follow-up and for any further evaluations that need to be completed.
 - The participant will discontinue the study drugs and be withdrawn from the study at that time.
- If the participant withdraws consent for disclosure of future information, the Sponsor may retain and continue to use any data collected before such a withdrawal of consent.
- If a participant withdraws from the study, it should be confirmed if he/she still agrees for existing samples to be used in line with the original consent. If he/she requests withdrawal of consent for use of samples, destruction of any samples taken and not tested should be carried out in line with what is stated in the informed consent and local regulation. The Investigator must document the decision on use of existing samples in the site study records and inform the Global Study Team.

7.3 Lost to Follow-up

A participant will be considered lost to follow-up if he or she repeatedly fails to return for scheduled visits and is unable to be contacted by the study centre.

The following actions must be taken if a participant fails to return to the study centre for a required study visit:

- The study centre must attempt to contact the participant and reschedule the missed visit as soon as possible and counsel the participant on the importance of maintaining the assigned visit schedule and ascertain whether or not the participant wishes to and/or should continue in the study.
- Before a participant is deemed lost to follow-up, the Investigator or designee must make every effort to regain contact with the participant (where possible, 3 telephone calls and, if necessary, a certified letter to the participant's last known mailing address or local equivalent methods). These contact attempts should be documented in the participant's medical record.
- Should the participant continue to be unreachable, he/she will be considered to have withdrawn from the study.
- Study centre personnel, or an independent third party, will attempt to collect the vital status of the participant within legal and ethical boundaries for all participants randomised, including those who did not get investigational product. Public sources may be searched for vital status information. If vital status is determined as deceased, this will be documented, and the participant will not be considered lost to follow-up. Sponsor personnel will not be involved in any attempts to collect vital status information.

7.4 Study Termination

AstraZeneca may terminate the entire study prematurely if concerns for safety arise within this study or in any other study with AZD5718. Discontinuation of specific sites or of the study as a whole are handled as part of [Appendix A](#).

8 STUDY ASSESSMENTS AND PROCEDURES

- Study procedures and their timing are summarised in the SoA ([Table 1](#)). Protocol waivers or exemptions are not allowed.
- Immediate safety concerns should be discussed with the Sponsor immediately upon occurrence or awareness to determine if the participant should continue or discontinue study drug.
- Adherence to the study design requirements, including those specified in the SoA, is essential and required for study conduct.
- All screening evaluations must be completed and reviewed to confirm that potential participants meet all eligibility criteria. The Investigator will maintain a screening log to record details of all participants screened and to confirm eligibility or record reasons for screening failure, as applicable.
- Procedures conducted as part of the participant's routine clinical management (eg, blood count) and obtained before signing of the ICF may be utilised for screening or baseline purposes provided the procedures met the protocol-specified criteria and were performed within the time frame defined in the SoA.
- The maximum amount of blood collected from each participant over the duration of the study, including any extra assessments that may be required, will be included in the ICF. Repeat or unscheduled samples may be taken for safety reasons or for technical issues with the samples.

8.1 Efficacy Assessments

8.1.1 Primary Efficacy Assessment

8.1.1.1 Urinary Albumin Creatinine Ratio

The urine ACR is a key marker for assessing kidney function. Urine ACR is a ratio between 2 measured substances (albumin and creatinine), which estimates 24-hour urine albumin excretion.

During this clinical study, a spot urine sample is collected during the Screening Visit 1 and at the remaining timepoints, participants are required to collect first morning void urine samples on 3 consecutive days (ideally day of visit and preceding 2 days [refrigerated overnight])

which are returned on the day of visit) as described in SoA (Table 1). If scheduled Visit 3 (Week 1) or Visit 7 (Week 12) will need to be delayed due to the need to repeat ABPM recording there is no need to repeat collection of the 3 urine samples. The containers to collect the urine samples are dispensed to the participant during Screening Visit 1 and as required at other visits during the course of the study. Urine ACR will be calculated as follows.

$$\text{Urine ACR (mg/g)} = \text{urine albumin (mg/dL)} / \text{urine creatinine (g/dL)}$$

At each visit, the geometric mean of the triplicate measurements will be computed centrally and used for all analyses of urine ACR.

8.1.2 Secondary Efficacy Assessments

8.1.2.1 Estimated Glomerular Filtration Rate

Estimated GFR is another marker that is considered as a standard for assessment of kidney function. It is calculated based on serum creatinine values using the widely validated and accepted CKD-EPI equation (Levey et al, 2009). Blood samples for estimation of serum creatinine are collected at various timepoints during the course of the study as shown in SoA (Table 1). Estimated GFR is then calculated as follows.

$$\begin{aligned} eGFR \text{ (mL/min/1.73 m}^2\text{)} \\ &= 141 \times \min(\text{Scr}/\kappa, 1)^\alpha \times \max(\text{Scr}/\kappa, 1) - 0.209 \times 0.993 \text{ Age} \\ &\times (1.018 \text{ if female}) \times (1.159 \text{ if Black}) \end{aligned}$$

Where: SCr = serum creatinine (in mg/dL); κ is 0.7 for females and 0.9 for males, α is -0.329 for females and -0.411 for males, min indicates the minimum of SCr/ κ or 1, and max indicates the maximum of SCr/ κ or 1.

Estimated GFR calculations will be performed by the central laboratory.

Alternatively, serum cystatin-C alone provides GFR estimates that are nearly as accurate as serum creatinine adjusted for age, sex and race thus providing an alternative GFR estimate that is not linked to muscle mass (Stevens et al, 2008). Blood samples will also be collected for measurement of cystatin-C at specified time points in the SoA (Table 1).

8.1.3

CCI

CCI [REDACTED]

CCI [REDACTED]

CCI [REDACTED]

[REDACTED]

8.2 Safety Assessments

Planned time points for all safety assessments are provided in the SoA ([Table 1](#)).

8.2.1 Physical Examinations

- A complete physical examination will be performed and include assessments of the following; general appearance, respiratory, cardiovascular, abdomen, skin, head and neck (including ears, eyes, nose, and throat), lymph nodes, thyroid, muscular-skeletal (including spine and extremities) and neurological systems.
- A brief physical examination will include, at a minimum, assessments of the skin, lungs, cardiovascular system, and abdomen (liver and spleen).

Physical examination will be performed at timepoints as specified in the SoA ([Table 1](#)).

8.2.2 Vital Signs

Vital signs will be performed at time points as specified in the SoA ([Table 1](#)). Vital signs will include BP, heart rate (HR), respiratory rate, body temperature, and pulse oximetry. Vital signs will be measured with the participant in a supine position having rested for at least 10 minutes before each reading and should be taken before any bloods draws. Vital signs should be

collected pre-dose on the days of study drug dosing and before blood draws. Blood pressure and pulse measurements will be assessed with a completely automated device. Manual techniques will be used only if an automated device is not available. Route of body temperature and pulse oximetry measurements will be conducted according to local procedures but should be consistent throughout the study for an individual participant.

8.2.3 Electrocardiograms

Triplicate 12-lead ECGs will be performed at timepoints as specified in the SoA, [Table 1](#) using an ECG machine that automatically calculates the heart rate and measures PR interval, QRS, QT, and QTc intervals.

The ECGs should be performed after the participant has rested for at least 10 minutes in supine position. Three individual ECG tracings should be obtained in succession, no more than 2 minutes apart. The full set of triplicates should be completed within 10 minutes.

The Investigator will make an overall evaluation of the ECG as normal or abnormal. If abnormal, it will be decided whether or not the abnormality is clinically significant or not clinically significant and the reason for the abnormality will be recorded on the eCRF. Abnormal values shall not be recorded as AEs unless deemed clinically significant. The printout of the ECG is to be signed, dated and filed in participant medical record as source document.

8.2.4 Clinical Safety Laboratory Assessments

A Laboratory Manual will be provided to the sites that specifies the procedures for collection, processing, storage, and shipment of samples, as well as laboratory contact information, specific to this clinical research study.

Blood and urine samples for determination of clinical chemistry, haematology, coagulation, and urinalysis will be taken at the visits indicated in the SoA ([Table 1](#)). Safety sampling will be done after at least 8 hours of fasting, except for Screening Visit 1.

Additional safety samples may be collected if clinically indicated at the discretion of the Investigator.

The clinical chemistry, haematology, coagulation, and urinalysis will be performed at the central laboratory, except for tests completed using urine dipsticks which will be done locally (see [Table 4](#) for details of these tests). Laboratory kits used locally will be provided by the central laboratory.

Where values for the following investigations are outside the usual range for a participant during screening, based on their medical history, retesting may be undertaken on one occasion without requiring a re-screen:

- Blood pressure, eGFR, spot urine for ACR, ALT, AST, bilirubin, serum potassium.

The following laboratory variables will be measured.

Table 4 Laboratory Safety Variables

Haematology/Haemostasis (whole blood)	Clinical Chemistry (serum or plasma)
B-White blood cell count	S/P-Sodium
B-Red blood cell count	S/P-Potassium
B-Haemoglobin	S/P-Urea
B-Haematocrit	S/P-Creatinine
B-Mean corpuscular volume	S/P-Creatine kinase
B-Mean corpuscular haemoglobin	S/P-Albumin
B-Mean corpuscular haemoglobin concentration	S/P-Calcium
B-Neutrophils absolute count	S/P-Phosphate
B-Lymphocytes absolute count	S/P-Glucose (fasting) (Non-fasting at Screening Visit 1)
B-Monocytes absolute count	S/P-Alkaline phosphatase
B-Eosinophils absolute count	S/P-Alanine aminotransferase
B-Basophils absolute count	S/P-Aspartate aminotransferase
B-Platelets	S/P-Total bilirubin
B-Reticulocytes absolute count	S/P-Follicle stimulating hormone ^{a,b}
Coagulation	S/P-Luteinising hormone ^{a,b}
B-International normalised ratio	S/P-Thyroid stimulating hormone (TSH)
B-Activated partial thromboplastin time	S/P-Free triiodothyronine (fT3)
B-Fibrinogen	S/P-Free thyroxine (fT4)
Urinalysis^c	S/P-Creatinine (for eGFR quantification)
U-Glucose (dipstick)	S/P-Chloride
U-Albumin (quantification/semi-quantification)	S/P-Bicarbonate
U-Glucose	S/P-Magnesium
U-Blood (dipstick)	S/P-Human chorionic gonadotropin hormone ^b
U-White blood cells	S/P-Albumin
U-human chorionic gonadotropin hormone (dipstick) ^b	S/P-Total protein
Other Clinical Safety Panels^a (serum or plasma)	
S/P-Hepatitis B surface Antigen	
S/P-Hepatitis C virus antibody	

Abbreviations: B = whole blood; eGFR = estimated glomerular filtration rate; P = plasma; S = serum; U = urine

^a Screening Visit 1 only

^b All women

- ° If urinalysis is positive for blood or white blood cells then microscopy through central laboratory, including white blood cells, red blood cells, and casts, should be completed

NOTE: In case a participant shows an AST or ALT $\geq 3 \times$ ULN together with total bilirubin $\geq 2 \times$ ULN please refer to [Appendix E](#). Actions required in cases of increases in liver biochemistry and evaluation of HL, for further instructions.

8.2.5 Ambulatory Blood Pressure Monitoring

24-hour ABPM will be performed at timepoints as specified in the SoA ([Table 1](#)). Participants will be provided the ABPM cuff and instructed to use the device 24 hours prior to the next visit.

Training for Application and Wearing of ABPM Device:

Participants will be given training at their local study site about how to set up and apply the ABPM device. In brief, an appropriate size BP cuff will be selected, and the device will be fitted to the nondominant arm of the participant, with the bladder placed over the artery and an initial test reading performed. The participants will be advised that for the first reading, the device will inflate to a pressure of 180 mmHg, and thereafter the device will adapt to inflate to a pressure just above the last recorded BP. The participant will be advised to undergo normal daily activities while wearing the cuff, and he/she will be advised to avoid any strenuous form of activity, bathing or showering while wearing the cuff. The participant will be advised to remain still during a measurement with the arm relaxed at heart level. The participant will also be given advice on how to wear the device during the day and at night while sleeping, and what to expect in terms of frequency of readings during the day and overnight. During ABPM, systolic BP, diastolic BP, heart rate pressure, HR, and mean arterial pressure readings will be recorded over a period of 24 hours. The participant may also visit the site for APBM cuff placement 1 day before their next assessment visit, as scheduled in the SoA ([Table 1](#)).

The site should ensure that the following validity criterion of the ABPM session is met prior to completing any other study assessments at the visit. An ABPM session may be repeated once if the following validity criterion has not been met:

- A minimum 20 h recording with at least 70% of expected measurements being successful
- If the validity criterion is not met, the associated study visit may be rescheduled to allow for a repeat ABPM recording only if the rescheduled visit can be completed within the specified tolerance period for study visits, as described in the SoA ([Table 1](#)).

If a repeat ABPM session is not possible, the study visit should proceed as indicated. In addition, the visit should also continue if the ABPM session does not meet validity criterion after the repeat session.

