4.9.3.3 Ambulatory Blood Pressure Monitoring

For drugs intended for chronic use, the US Food and Drug Administration (FDA) recommended use of ambulatory blood pressure monitoring (ABPM) to assess the sustained BP effect ([FDA guidance on Assessment of Pressor Effects of Drugs, May 2018](#)). The collection and the analysis of the ABPM data in this study is aimed to delineate differential BP effect of AZD5718 relative to placebo.

The device will be provided to the participants at the visits outlined in the SoA in [Appendix A](#) (Screening Visit 2 and Visit 6 [Week 8]). They will be instructed to perform the ABPM 24-hours before their next visit, ie, Visit 3 (Week 1) and Visit 7 (Week 12), respectively. The ABPM recording must have finished prior to dosing at each specified visit.

If the 24-hour ABPM assessment session provided at a visit is confirmed to not meet the validity criteria, the associated study visit may be rescheduled to allow for a repeat ABPM recording only if the rescheduled visit can be completed within the specified tolerance period for study visits, as described in the SoA in [Appendix A](#). An assessment session is valid if there is a minimum of 20 hours of the recording with at least 70% of expected measurements being successful. If the repeated assessment session is not valid using the same validity criteria, no further repeats will be performed for that visit. This criterium for the validity of measurements will only be used on site to reschedule the ABPM assessment session. The inclusion criteria for the statistical analysis are separate and are described in the following paragraph.

Recordings will be done every 20 minutes during the day-time (06:01 to 22:00) and every 30 minutes during the night-time (22:01 to 06:00). These definitions of day-time and night-time are only to be used on site for collecting recordings; they will be defined differently for the purpose of statistical analyses.

For the purpose of inclusion in the statistical analyses, the session needs to satisfy two conditions:

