1. There should be at least 50% of successful measurements in both day-time (06:01 to 22:00) and night-time (22:01 to 06:00). If both the scheduled and repeat assessment sessions have more than 50% of successful measurements in the respective timeframes, the assessment session with a higher overall percentage of successful measurements will be included in the analyses. In the unlikely event that both the scheduled and repeated assessment sessions have the same percentage of successful measurements (and both above 50%), the scheduled assessment session will be taken as the visit assessment.
2. There are not more than two consecutive hours with no available measurements in an ABPM assessment session.

Primary ABPM Analysis

The primary endpoint in the analysis is the change from baseline in 24-hour mean SBP at Week 12. Participants with missing mean 24-hour SBP at Week 12 will be excluded from the analysis.

In order to derive the mean SBP over various time periods, the hourly mean SBP is derived for each participant for each hour using the available data at the visit. This is the sum of the successful non-missing SBP measurements in the hour, divided by the number of non-missing SBP measurements in the respective hour. This derivation will be used to further derive the endpoints of interest.

The 24-hour mean SBP is derived as the sum of the non-missing hourly mean SBP measurements, divided by the number of hours with non-missing hourly mean SBP. Missing hourly mean SBP derivations will not be counted towards the 24-hour mean.

For the ABPM analysis, baseline for the 24-hour mean ABPM parameter (or mean day-time, mean night-time, mean hourly) is defined as the 24-hour mean value (or corresponding mean day-time value, mean night-time value, mean hourly value) during the Screening Visit 2.

The change from baseline in 24-hour mean SBP at Week 12 will be analysed using an ANCOVA model, with change from baseline in 24-hour mean SBP as the dependent variable, adjusting for DM stratification factor, treatment group (AZD5718 **CC** mg, AZD5718 **CC** mg, AZD5718 **CC** mg, placebo), plus baseline 24-hour mean SBP and BMI as covariates. The ambulatory blood pressure monitoring population will be used for this analysis. The least squares (LS) mean difference between each of the AZD5718 doses and placebo (ie, placebo-corrected change from baseline in 24-hour mean SBP) will be derived from the model. The 2-sided 90% CI for these differences will be presented.

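### An ambulatory BP session can pass the site's validity check, trigger no repeat, and then be excluded by the SAP's separate entry test

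*Protocol*

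**What the plan says.** **On site.** Protocol 8.2.5 sets one validity criterion: "A minimum 20 h recording with at least 70% of expected measurements being successful". The repeat depends on it: "An ABPM session may be repeated once if the following validity criterion has not been met". Footnote o of the Schedule of Activities ties rescheduling to the same criterion. For Visit 3 it allows up to 72 hours after the scheduled visit and at most 32 days from Screening Visit 1. For Visit 7 it allows 72 hours either side of Day 85.

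**In the analysis.** SAP 4.9.3.3 restates the site criterion and limits its role: "This criterium for the validity of measurements will only be used on site to reschedule the ABPM assessment session". It continues: "The inclusion criteria for the statistical analysis are separate and are described in the following paragraph". Two conditions then govern entry:

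1. "There should be at least 50% of successful measurements in both day-time (06:01 to 22:00) and night-time (22:01 to 06:00").
2. "There are not more than two consecutive hours with no available measurements in an ABPM assessment session".

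Condition 1 also holds the rule for choosing between a scheduled and a repeat session. If both exceed 50% in each timeframe, the one with the higher overall success percentage is used.

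**Consequence of failing entry.** "Participants with missing mean 24-hour SBP at Week 12 will be excluded from the analysis". The ABPM population in SAP 4.5 needs valid data for a change from baseline, so the baseline session matters as well.

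**Schedule of readings.** This appears only in the SAP: "Recordings will be done every 20 minutes during the day-time (06:01 to 22:00) and every 30 minutes during the night-time (22:01 to 06:00").

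**The concern.** The single repeat is the plan's only means of rescuing a poor recording. It is tied to an overall percentage, whereas the analysis looks at the night separately and at gaps. Night readings are a quarter of the total, so a good day can carry a poor night past the site check. The site then has no provision for a repeat, even if the visit window is still open, and the session is discarded later.

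Change in 24-hour mean SBP at Week 12 is a listed secondary endpoint, which protocol 4.2.2 says was included in line with an FDA recommendation. Day-time and night-time means are secondary ABPM endpoints. Edition 2 of the SAP had added multiple imputation for ABPM data. Edition 3 removed the ABPM sensitivity analysis, leaving a summary of missingness. Participants lost this way are therefore simply absent from the ANCOVA.

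**Working it through.** The documents give no SD, expected missingness or power for 24-hour SBP, so there is no stated figure to reproduce. The check is a count of readings.

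**Inputs (SAP 4.9.3.3, protocol 8.2.5)**
- Day: 16 h × 3 per hour = 48. Night: 8 h × 2 per hour = 16. Total 64.
- Site threshold: 0.70 × 64 = 44.8, so 45 readings, with at least 20 h recorded.
- SAP condition 1: at least 24 of 48 by day and 8 of 16 by night. Condition 2: no gap over 2 h.

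**Sessions that pass on site and fail SAP entry**

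| Session | Overall | Site check | SAP entry |
|---|---|---|---|
| 48 day + 7 night | 55/64 = 85.9% | pass | fails condition 1: night 7/16 = 43.8% |
| One 3 h night gap (6 readings lost) | 58/64 = 90.6% | pass, 21 h with data | fails condition 2 |
| One 3 h day gap (9 readings lost) | 55/64 = 85.9% | pass, 21 h with data | fails condition 2 |

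None of these depends on whether 20 h means recorder span or hours containing readings.

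**How general this is.** For a given night count n, the day counts that reach 45 run from 45 − n to 48, which is 4 + n values.
- All n from 0 to 16: 17 × 4 + 136 = 204 combinations meet 70%.
- n from 0 to 7: 8 × 4 + 28 = 60 of these fail the night rule.
- None fails the day rule: even with 16 night readings, 45 − 16 = 29 day readings are needed, above 24.

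The reverse also occurs. For n from 8 to 16, day counts from 24 to 44 − n meet the SAP counts but miss 70%. That is 21 − n values each, 13 + 12 + … + 5 = 81 combinations. These are counts of combinations, not probabilities.

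**Choosing between two sessions**
- Scheduled: 32 day + 12 night = 44/64 = 68.75%, no long gap. It fails on site, but meets both SAP conditions (day 32/48 = 66.7%, night 12/16 = 75%).
- Repeat: one 3 h night gap, 58/64 = 90.6%. It meets condition 1 (night 10/16 = 62.5%) but fails condition 2.

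Read literally, condition 1 selects the repeat on its higher percentage, and condition 2 then removes it. A usable session is lost.

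**Size, by assumption only.** Let f be the share of sessions at one visit that pass on site and fail entry. Take the planned 142 evaluable per group as an illustrative base. Loss = 142f, and relative CI width = 1/√(1 − f). Recovery assumes that 50–80% of repeats succeed.

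| f (assumed) | Lost per group | CI width | Recoverable |
|---|---|---|---|
| 2% | 2.8 | × 1.010 | 1.4–2.3 |
| 5% | 7.1 | × 1.026 | 3.6–5.7 |
| 10% | 14.2 | × 1.054 | 7.1–11.4 |

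**The case against.** **The separation is declared.** The SAP says outright that the site check serves rescheduling only and that the analysis rules are separate. That stands: this is not a hidden contradiction. But declaring two rules separate does not explain why the repeat should be withheld from sessions that the analysis will reject.

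**No sentence forbids repeating a passed session.** Also true. The restriction is inferred from a permission given only when the criterion is not met, together with the bar on protocol waivers in protocol section 8. The safe statement is that nothing provides for such a repeat.

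**The mismatch runs both ways.** The SAP counts are also more lenient than 70% in some combinations, so some repeats are triggered that the analysis does not need. Adding conditions to the trigger leaves that inefficiency in place.

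**The loss will be visible.** SAP 4.9.3.3 summarises missingness against its entry criteria by treatment group and key baseline characteristics. This describes the loss but does not reduce it, and it does not separate out the sessions that had passed on site.

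**A larger loss might be inferred.** Because both baseline and Week 12 are needed, a reader might take 5–10% per session and compute 1 − (1 − f)² = 9.75–19% of participants lost, all of it avoidable. The documents do not support this. The rate has no source. The formula assumes independent failures at the two visits; if the same people record poorly both times, the loss can be as low as f. And not every repeat would succeed.

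**Conclusion.** The mismatch holds on the documents' own rules, provided that sites used the SAP's reading schedule. Sessions scoring 86–91% overall can pass on site, trigger no repeat and be excluded, at baseline or at Week 12. The failures come from the night-time 50% rule and the two-hour gap rule; the day-time 50% rule never bites once 70% is reached. The session-choice rule has a related defect: it can discard a usable scheduled session.

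The size is unknown. For an assumed 2–10% of sessions at one visit, about 3–14 of 142 per group would be lost and intervals would be 1–5% wider, with only part of that recoverable.

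A reader might also infer a biased treatment comparison, since the night rule selects against poor night recordings. The documents show no link between recording failure and arm, so the supported conclusion is an avoidable loss of data on a secondary endpoint.

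**What to change.** 1. **Repeat trigger (protocol 8.2.5 and footnote o of the Schedule of Activities, repeated in SAP Appendix A).** Add the two SAP entry conditions to the existing criterion, so that a session failing any of them qualifies for the one repeat within the present visit tolerance. No session that passed on site could then fail SAP entry. The cost is a few more rescheduled visits and, in a running study, a protocol amendment. SAP edition 3 post-dates the early termination, so this cannot recover data here; it is a correction for a protocol reusing this text.

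2. **Session choice (SAP 4.9.3.3).** Apply both conditions to each session first, then choose by overall percentage only among sessions meeting both. This is a wording and programming change that needs no new data.

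3. **Reporting.** Give, by arm and for baseline and Week 12, the number of sessions that passed on site but failed SAP entry. Add a sensitivity ANCOVA that includes them. The SAP averages the non-missing hourly means, so a 24-hour mean can still be derived for these sessions; where night hours are empty that mean leans towards day-time values, and the report should say so. The cost is one table and one model run.
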